Registration	The study will be registered with ClinicalTrials.gov
Background and purpose	The diagnosis of LHCF is complicated by radiographic inability to show the full extent of the injury into the chondral (unossified) epiphysis. MRI gives a perfect view of these fractures. The safety and feasibility of non-operative treatment based on MRI findings in children with elbow fractures has not been investigated in a Danish setting. If safe and feasible, the use of MRI could dramatically lower the need for surgery in children with LHCF.
Condition	Pediatric lateral humeral condyle fracture
Intervention/procedure investigated	Non-operative treatment of LHCF based on MRI findings
Comparison	None
Study type	Interventional
Study design	Prospective, Cohort, Single center
Short description	Cohort study of 50 patients aged 2-15 with acute LHCF. Intervention with non-operative treatment based on MRI performed without sedation or anesthesia. Objectives are to describe functional outcome, radiological healing, secondary fracture displacement and any complications after two years. Patients are seen for follow-up 1, 2 and 4 weeks and 3, 6, 12 and 24 months after injury. The investigators hypothesize that undisplaced and minimally displaced LHCF can be treated non-operatively based on MRI findings with good functional outcomes after two years.
Primary objective	Describe the functional outcome two years after non-operative treatment of undisplaced and minimally displaced LHCF in children.
Secondary objectives	
 Describe the feasibility of performing a subacute MRI of the elbow in children with LHCF within 2-7 days after the injury without sedation or anesthesia Report MRI findings and classify fractures according to Song classification based on MRI Report the number and proportion of fractures that displace secondarily and their treatment Report final treatment; non-operative or operative Describe radiographic results and compare with MRI Report any early or late complications

Hypothesis	Children with minimally displaced LHCF (Song stage 1, 2 and 3) can be treated non-operatively based on MRI findings with good functional outcome after two years.
Primary outcome measure	Mayo Elbow Performance Score (MEPS) two years after injury

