Secondary outcome measures	
 • Pain • Radiographic results • MRI results • Alteration in treatment regime based on MRI • Number and proportion of fractures with secondary displacement • Any early or late complications
Statistical considerations and estimated enrollment	
Sample size is estimated from previous studies which included less than 30 participants. The investigators of this study suspect that by enrolling 50 participants the age distribution and variation in fracture pattern will be representative of the background population.
 
Baseline characteristics and outcomes recorded at scheduled FU assessments will be presented using simple summary statistics.

Start of enrollment	October 2021 (estimated)
Last patient/last visit	October 2025 (estimated)
Eligibility inclusion criteria	
Inclusion criteria:
 
 • Children age 2-15 years • Diagnosis of acute LHCF (<5 days) with <5 mm of displacement on plain radiographs • Parental informed consent obtained
Eligibility exclusion criteria	
Exclusion criteria:
 
 • Contraindication(s) to performing an MRI • Unable to participate in follow-up • Existing bone pathology • Previous ipsilateral elbow fracture
Principal Coordinating Investigator	
[name] Department of Orthopedic Surgery Copenhagen University Hospital – Herlev and Gentofte Copenhagen, Denmark
 
[contact] [contact] E-Mail [contact]

Study site	
Department of Orthopedic Surgery Copenhagen University Hospital – Herlev and Gentofte Copenhagen, Denmark

Health authority	
The Danish Data Protection Agency The Danish National Committee On Health Research Ethics

Pubmed Medical Subject Heading [MeSH] terms and keywords
	
Child [MeSH] Casts, Surgical [MeSH] Fracture Fixation [MeSH] Humeral Fractures [MeSH]

Imaging review
	
All images collected will be analyzed by independent radiologists during the study

96

97

98 2 Rationale and purpose of the study

99 The treatment of LHCF is most often surgical with open reduction and fixation [1]. The diagnosis of
100 LHCF is complicated by radiographic inability to show the full extent of the injury into the unossified
101 chondral epiphysis and therefore physicians often opt for open surgical treatment. MRI; however, gives
102 a perfect view of these fractures [2–5]. This project investigates the safety and feasibility of non-

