171 Stage 1 and 2 fractures are considered stable and can be treated non-operatively. Stage 3 fractures are
 172 complete and traverse the entire course of the metaphysis, chondroepiphysis and the articular cartilage
 173 leaving the fragment without any attachment. These fractures can be undisplaced but are always
 174 considered unstable. Treatment controversy arises from the inability to distinguishing stage 1 and 2
 175 from stage 3 on plain radiographs.
 176

[figure not shown]

177
 178
 179

Figure 1 - Song classification.

180 Because of the risk of secondary displacement, operative treatment is often conducted with many
 181 surgeons choosing open reduction and fixation in all cases [19,20]. Operative fixation imposes the risk
 182 of minor complications such as superficial infection, ulcers and granulomas but also major complications
 183 such as deep infection, osteomyelitis, malunion, non-union, growth disturbance and osteonecrosis [21].
 184

185 MRI with specific cartilage sequences (figure 2) can clearly show the chondroepiphysis and studies
 186 have shown that MRI is capable of precisely showing the fracture pattern [2,3,5,22]. Using simple
 187 techniques and advances in technology to prepare the child, MRI has been shown to be feasible in
 188 younger children without sedation or anesthesia in whom this was previously thought necessary [23–
 189 30].
 190

191
 192
 193
 194

Figure 2 - MRI showing LHC. Left: Stage 1, confined to metaphysis. Center: Stage 2, fracture line stops in the chondroepiphysis. Right: Stage 3, traverses the joint cartilage.

195

196 5 Primary and secondary objectives

197 5.1 Primary objective

198

199 To describe the functional outcome two years after non-operative treatment of undisplaced and
200 minimally displaced LHCF in children.

201 5.2 Secondary objective(s)

202

- 203 • Describe the feasibility of performing a subacute MRI of the elbow in children with LHCF within 2-7
- 204 days after the injury without sedation or anesthesia
- 205 • Report MRI findings and classify fractures according to Song classification based on MRI
- 206 • Report the number and proportion of fractures that displace secondarily and their treatment
- 207 • Report final treatment; non-operative or operative
- 208 • Describe radiographic results and compare with MRI
- 209 • Report any early or late complications

210 5.3 Hypothesis

211

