212 Children with minimally displaced LHCF (Song stage 1, 2 and 3) can be treated non-operatively based
213 on MRI findings with good functional outcome after two years.

214 6 Study design

215 This project uses a cohort study design conformed to the STROBE Statement [31]. The investigators
216 aim to prospectively and consecutively recruit all children with undisplaced or minimally displaced LHCF
217 (cohort) which based on MRI are treated non-operatively (exposure). We report functional and
218 radiological outcome two years after the injury (outcome). This study design is relevant in reporting the
219 primary and secondary outcomes based on the exposure in our cohort.

220 6.1 Study population and patient enrollment

221

222 This study investigates the treatment of pediatric LHCF; therefore, this study cannot be conducted in
223 consenting adults. LHCF occur predominantly in 4-9 year olds and thus it is not possible to select only
224 older children for inclusion.

225

226 This study is believed to have great positive implications for the participants and successive patients
227 with the same condition.

228 6.1.1 Setting

229

230 The study will be performed in the Capitol Region of Denmark. Patients in the catchment area of
231 Copenhagen University Hospital – Herlev and Gentofte are eligible for recruitment (population 700.000
232 of which 80.000 are children).

233 6.1.2 Inclusion criteria

- 234 • Children aged 2-13 years
- 235 • Diagnosis of acute LHCF
 - 236 – Fracture <5 days old
 - 237 – Fracture with <5 mm of displacement on plain radiographs (AP, ML and IO views)
- 238
- 239 • Parental informed consent obtained:
 - 240 – Ability of all legal guardians to understand the content of the patient information and ICF
 - 241 – Willingness and ability to let the child participate in the clinical investigation according to the
 - 242 Clinical Investigation Plan (CIP)
 - 243 – Signed and dated EC-approved written parental informed consent sheet

244 6.1.3 Exclusion criteria

- 245 • Contraindication(s) to performing an MRI [32] without the use of sedation or anesthesia:
 - 246 – Ferromagnetic implants or foreign bodies
 - 247 – Pacemaker
 - 248 – Ear implant
 - 249 – Severe claustrophobia
- 250 • Unable to participate in follow-up
- 251 • Existing bone pathology
 - 252 – Tumor
 - 253 – Osteogenesis imperfecta
 - 254 – Degenerative disease
- 255 • Previous ipsilateral elbow fracture

256 6.1.4 Enrollment of participants

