 291 system. Parents are usually very keen to take their children for follow-up appointments making the risk
 292 of missing an appointment low. Any participants who miss an appointment will be contacted by phone to
 293 reschedule.

294

295 Table 1: Study schedule

296

Assessment parameters	Out-patient clinic visits and imaging procedures *										
	Visit 1**	Visit 2	Visit 3	Visit 4	Visit 5	Visit 6	Visit 7	Visit 8	Visit 9	Visit 10	
	Injury (day 0)	Screening	Information visit	Enrollment and consent	5 (± 3) days	12 (± 3) days	4 weeks	3 months	6 months	12 months	24 months
Eligibility	X										
Patient information		X									
Consent			X								
Demographics			X								
MRI				X							
If applicable - Control-MRI					(X)						
Cast removal***						X					
Radiographs and clinical exam					X	X	X	X	X	X	

297

298 * All FU visits with the defined time windows are calculated from the day of injury (i.e. day 0).

299 ** Telephone interview.

300 *** Casting may be prolonged two weeks in case of lack of callus formation at four weeks.

301

302 6.2.1 Visit 1: Screening (by phone)

- 303 • As described in section 6.1.4, the parents of potential study patients are informed about the study
304 over telephone by the PI.

305 6.2.2 Visit 2: Information visit

- 306 • All inclusion and exclusion criteria are checked to decide if the patient can participate in the study.
307 • Specific procedures for enrollment of pediatric patients are undertaken. A more detailed description
308 of the enrolment of participants and informed consent process is provided in section 6.1.4 and 10.
309 • Before any study-specific examinations are performed, the patient's parents give written informed
310 consent to participate in the study according to the CIP.

311 6.2.3 Visit 3: Enrolment, consent and preparation for MRI

- 312 • Obtain baseline demographics
313 • Book MRI
314 • Prepare child for MRI using the Child Centered Care model described in section 6.3
315 • Data verification and entry into the eCRF

316 6.2.4 Visit 4: MRI (5 (± 3) days)

- 317 • The MRI is performed according to the Child Centered Care model described in section 6.3
318 • Results of the MRI are given to the parents by phone
319 • Any necessary adjustments to the treatment plan is made
320 • Entry into the eCRF

321 6.2.5 ONLY if applicable: Control-MRI (12 (± 3) days)

- 322 • If an unstable Song stage 3 fracture is diagnosed based on the initial MRI an additional control MRI

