456 **Figure 5 - Modified Mayo Elbow Performance Score.**
 457

458

459 **7.2 Secondary outcomes**

460 **7.2.1 MRI results**

- 461 • Proportion of successful MRIs defined as a completed scan with an image quality that is useful for
- 462 analysis by the radiologist.
- 463 • MRI findings.
- 464 • Song classification based on MRI.
- 465 • Scan length (minutes).
- 466 • Any discomforts for the child during the scan.

467 **7.2.2 Radiographic results**

468 Injury radiographs and subsequent radiographs during FU will be read and described by a senior
 469 orthopedic surgeon.

470 **7.2.3 Secondary displacement**

471 Any secondary displacement and amount of radiographic displacement (mm) is recorded.

472 **7.2.4 Pain**

473 To quantify pain in the patient, an age appropriate rating scale is applied:

- 474 • Age <5 years: Face, Legs, Activity, Cry, Consolability Scale (FLACC)
- 475 • Age >4 years: Faces Pain Scale – Revised (FPS-R)
- 476 • Age >8 years: Visual analogue scale

477 **Face, Legs, Activity, Cry, Consolability Scale (FLACC)**

479 To quantify pain behaviors in children who may not be able to verbalize the presence or severity of pain
 480 FLACC [38] provides a simple framework. The child is observed for at least 2-5 minutes. Legs and body
 481 are observed uncovered. Activity is observed and body is assessed for tenseness and tone.

482

Behavior	0	1	2
Face	No particular expression or smile	Occasional grimace or frown, withdrawn, disinterested	Frequent to constant quivering chin, clenched jaw
Legs	Normal position or relaxed	Uneasy, restless, tense	Kicking or legs drawn up
Activity	Lying quietly, normal position, moves easily	Squirming, shifting, back and forth, tense	Arched, rigid or jerking
Cry	No cry (awake or asleep)	Moans or whimpers; occasional complaint	Crying steadily, screams, sobs, frequent complaints
Consolability	Content, relaxed	Reassured by touching, hugging or being talked to, distractible	Difficult to console or comfort

483

484 Assessment of Behavioural Score:

- 485 • 0 = Relaxed and comfortable
- 486 • 1-3 = Mild discomfort
- 487 • 4-6 = Moderate pain
- 488 • 7-10 = Severe discomfort/pain

489

[figure not shown]
490

491

492

493 Faces Pain Scale – Revised (FPS-R)

494 The Faces Pain Scale – Revised (FPS-R) [39] is used to quantify pain in children above four years of
 495 age. It is a self-report measure of pain intensity developed for children. It was adapted from the Faces

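### Excluding children with severe claustrophobia biases the unsedated-MRI success proportion upward relative to all children with LHCF, by an amount that is unknown and may be small or zero

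*Protocol*

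**What the plan says.** **Objective and outcome.** The secondary objective in section 5.2 is to "Describe the feasibility of performing a subacute MRI of the elbow in children with LHCF", in the first days after injury and without sedation or anesthesia. Section 7.2.1 measures it as "Proportion of successful MRIs defined as a completed scan with an image quality that is useful for" radiological reading. The primary outcome is a different one: "Mayo Elbow Performance Score (MEPS) two years after injury" (Synopsis).

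**Exclusion.** The Synopsis lists "Contraindication(s) to performing an MRI" and gives no examples. Section 6.1.3 words it as "Contraindication(s) to performing an MRI [32] without the use of sedation or anesthesia" and names four items: ferromagnetic implants or foreign bodies, pacemaker, ear implant, and "Severe claustrophobia".

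**Timing and records.** Eligibility is asked about by phone (section 6.1.4). At Visit 2, "All inclusion and exclusion criteria are checked to decide if the patient can participate in the study" (section 6.2.2). The Child Centered Care preparation starts at Visit 3 and the MRI is Visit 4. Section 6.1.4 states that nothing from the phone pre-screening is recorded for the study, and it describes database entry for children whose parents have consented.

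**Bias statement.** Section 9 expects a representative cohort and rates the overall risk of bias as low. It does not mention this exclusion.

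**The concern.** Three of the four listed items are scanner-safety reasons, which sedation would not change. Severe claustrophobia is different: it concerns whether the child can tolerate the scanner while awake, and that is what section 7.2.1 measures. On this item, eligibility is decided partly on the expected outcome.

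A child excluded for this reason never receives the preparation and enters neither the numerator nor the denominator. The result then describes children without severe claustrophobia, while the objective is stated for children with LHCF. Because the phone pre-screening is not documented, the final report could not say how many children this concerns. A later analysis plan could not recover the number either.

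At stake is what the feasibility result may claim. Section 2 bases the hoped-for reduction in surgery on MRI done awake, so the share of children who can be scanned this way is of practical interest.

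**Working it through.** **No figure to reproduce.** The protocol gives no target or expected value for the success proportion, and the sample size of 50 comes from no formula. The only reference value is the earlier study cited in section 10: 25/27 = 92.6%.

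**Inputs**
- Planned enrolment: 50 (section 6.1.4).
- Successful scans among enrolled children: assumed 46, so p = 46/50 = 92.0%, close to the cited 92.6%.
- k, otherwise eligible children excluded for severe claustrophobia: not given; shown for 0 to 10.
- f, the share of those k who would have succeeded if prepared and scanned: not given; shown for 0 (worst case) and 0.5.

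**Formulas**
- Proportion with the excluded children included: (46 + f·k) / (50 + k).
- Overstatement: 46/50 − (46 + f·k)/(50 + k) = k·(p − f)/(50 + k).

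The overstatement is positive whenever k > 0 and f < p, that is, whenever these children would succeed less often than enrolled children. It is zero when k = 0.

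| k | f = 0 | Overstatement (points) | f = 0.5 | Overstatement (points) |
|---|---|---|---|---|
| 0 | 46/50 = 92.0% | 0 | 92.0% | 0 |
| 1 | 46/51 = 90.2% | 1.8 | 46.5/51 = 91.2% | 0.8 |
| 3 | 46/53 = 86.8% | 5.2 | 47.5/53 = 89.6% | 2.4 |
| 5 | 46/55 = 83.6% | 8.4 | 48.5/55 = 88.2% | 3.8 |
| 10 | 46/60 = 76.7% | 15.3 | 51/60 = 85.0% | 7.0 |

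Moving from f = 0 to f = 0.5 multiplies the overstatement by (0.92 − 0.5)/0.92 = 0.46, so it is roughly halved.

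**Sampling error for comparison.** The exact 95% interval for 46/50 is 80.8% to 97.8%. The worst-case figures for k = 1, 3 and 5 all lie inside it.

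**Which failures are still counted.** Section 6.1.3 lists no general item for anxious, uncooperative or very young children, so they can be enrolled. If their scan fails, section 6.3.5 ends their participation, but nothing there or in section 7.2.1 takes the failed scan out of the count. The loss is therefore confined to children screened out before enrolment.

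**The case against.** The case against has several parts, and most of them limit the point.

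- A reader might infer that section 6.1.3 removes every child expected to fail an awake scan. It does not. Only one of its four items concerns tolerance. The open wording about sedation could be read more widely, but the list does not do so. This narrows the point to severe claustrophobia.
- A reader might infer that the Synopsis sets a narrower criterion limited to implants and devices. It contains no list, and its short phrase may summarise the same four items. Section 6.1.3 cites a source for its criterion that is not available here, so whether claustrophobia belongs among contraindications cannot be settled from the protocol.
- Counting children who were never prepared or scanned as failures presumes the answer. That is correct, so such a figure is a lower bound and not a corrected estimate.
- The size is assumed throughout. Five such children beside 50 enrolled would be 5/55 = 9% with severe claustrophobia, and nothing in the protocol supports a rate that high.
- The outcome is secondary and descriptive, with no threshold or decision attached, and the proportion is valid for children who meet the criterion. This limits the importance of the point. It does not remove the mismatch with an objective stated for children with LHCF, or the fact that the number excluded cannot be reported.

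**Conclusion.** The concern holds in a limited form. Excluding severe claustrophobia before preparation and scan biases the section 7.2.1 proportion upward relative to children with LHCF, provided that at least one otherwise eligible child is excluded for this reason and that such children would succeed less often than those enrolled. As section 6.1.4 stands, the report could not show how many were lost.

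The size is unknown and may be small or zero. Under the assumed 46/50, the overstatement for one to five excluded children runs from 0.8 to 3.8 points if half would have succeeded, and from 1.8 to 8.4 points if none would. A reader might infer that the study's main result is compromised. The protocol does not support that: two-year MEPS is not directly affected. The point changes what the feasibility result can claim, and section 9's low-bias rating should acknowledge it.

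**What to change.** The enrolment exclusion may stay, and no additional child needs to be scanned.

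1. **Section 6.1.4:** replace the statement that pre-screening is undocumented with an anonymous count, with reason, of otherwise eligible children excluded by phone or at Visit 2 because an unsedated scan was judged impossible. The reason can be taken from the conversation with the parents, so the bar in section 14 on study access to records before consent is respected.
2. **Section 7.2.1:** report the success proportion twice: among enrolled children, and with the counted children added to the denominator as not scanned. Label the second figure a lower bound with respect to this exclusion. Children excluded for implants or devices stay out of both.
3. **Conclusion:** word feasibility for children without severe claustrophobia, unless the second figure is the one used.

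The cost is one anonymous tally, a changed sentence in section 6.1.4 handled as an amendment under section 21, and possibly a slightly less favourable figure. No extra visit or procedure is needed.

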323 is performed during this visit
324 • Results of the MRI are given to the parents by phone
325 • Any necessary adjustments to the treatment plan is made
326 • Entry into the eCRF

327 6.2.6 Visit 5: Radiographs and clinical examination (12 (± 3) days)

- 328 • Plain radiographs of injured elbow without cast (AP, ML and IO)
329 • Clinical examination
330 – Cast condition
331 – Assessment of pain and use of pain medication
332 – Neurovascular status of the hand
333 • Entry into the eCRF

**334 6.2.7 Visit 6, 7, 8, 9 and 10: Radiographs and clinical examination (4 weeks and 3, 6, 12 and 24
335 months).**

- 336 • Plain radiographs of injured elbow without cast (AP, ML and IO)
337 • Clinical examination
338 – Assessment of pain and use of pain medication
339 – Neurovascular status of the hand
340 – Bilateral elbow assessment according to Mayo Elbow Performance Score (MEPS)
341 – Bilateral carrying angle of the elbow measured in degrees by goniometer
342 • Entry into the eCRF

343 **6.2.8 Unscheduled visits**

344 Unscheduled visits can take place at any time during the study if a need occurs or if the investigator
345 considers this to be appropriate for patient care. Information collected between study visits are to be
346 documented at the next regular study visit with the following exceptions:

- 347 • If a patient drops out of the study, a dropout form is completed at the time of dropout

348 **6.2.9 Premature study termination**

349 Patient participation in the study may end prematurely for one of the following reasons:

- 350 • Patient withdrew informed consent
- 351 • Protocol violation
- 352 • Investigator's discretion (e.g. patient noncompliance with CIP)
- 353 • Unknown/lost to FU

354

355 For each case of premature termination detailed information will be obtained explaining the
356 circumstances leading to the termination. This will be recorded on a dropout form in the eCRF.

357

358 If patients are withdrawn from the study, any collected data will be censored. Censoring allows this
359 collection of data to be accounted for in the analysis.

360 **6.3 Study treatments**

361

362 This study is not investigating any medical device. All devices in this study will be used per standard of
363 care at the participating institutions.

364 **6.3.1 Emergency treatment**

365 All patients who sustain a LHCF are initially treated in the ED with an above elbow splint. Parents and,

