 496 Pain Scale [40] to make it possible to score the sensation of pain on a 0-to-10 metric. The scale shows
 497 a close linear relationship with visual analog pain scales (VAS) across the age range of 4-16 years.
 498

[figure not shown]

499
 500 **Figure 6 - Faces of the FPS-R. The child is instructed to point to the faces that shows how much pain the child is in at**
 501 **that moment. Faces are scored 0, 2, 4, 6, 8 or 10 from left to right.**

502
 503 FPS-R is easy to administer and requires no equipment except for the photocopied faces (figure 6). The
 504 child is asked to point to the face that shows how much pain the child is in at that moment. Faces are
 505 scored 0-10 so 0 equals no pain and 10 equals very much pain.
 506

507 Visual analogue scale

508 A visual analogue scale (VAS) (Figure 7) is used to quantify pain in children age 8 and above. VAS has
 509 been extensively investigated in quantifying pain in older children [41,42]. The child is asked to put a
 510 mark on the line corresponding to the child's pain at that moment. A mark to the far left equals no pain
 511 and a mark to the far right equals worst possible pain. The line is 10 cm long and the child's mark is
 512 measured from left to right in cm with one decimal e.g., 3.4 cm equaling a VAS of 3.4. If the child cannot
 513 cooperate to using VAS, FPS-R is used instead.
 514
 515

516
 517 **Figure 7 - Visual analogue scale (VAS) for quantifying pain in children age 8 and above.**

518
 519
 520
 521
 522

523 8 Statistical planning

524 8.1 Hypotheses

525

526 Minimally displaced LHCF (Song stage 1, 2 and 3) can be treated non-operatively based on MRI
527 findings with good functional outcomes after two years.

528 8.2 Sample size considerations

529

530 Samples size is estimated from previous studies which included less than 30 participants [22,23]. The
531 investigators of this study suspect that by enrolling 50 participants the age distribution and fracture
532 pattern variation will be representative of the background population. By enrolling 50 patients the
533 investigators suspect that any frequent and serious complications will be found.

534 8.3 Statistical analysis

535

536 Baseline characteristics and outcomes recorded at scheduled FU assessments will be presented using
537 simple summary statistics.

538

- 539 • Categorical variables will be summarized using the frequency and percentage for each category.

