- 540 • Continuous variables will be summarized using the mean, standard deviation (SD), median, inter-
541 quartile range, and minimum and maximum values and, if appropriate, according to clinically relevant
542 categories.

543

544 In general, continuous variables with both baseline and FU measurements available will also be
545 summarized in terms of the individual patient-level changes between baseline and follow-up.

546

547 A p-value of <0.05 is regarded as being significant. Data will be analyzed using SPSS (SPSS, Chicago,
548 IL, USA).

549 8.3.1 Patient discontinuation

550

551 If a participant chooses to discontinue the follow-up examinations for any reason, the date and reason
552 for drop-out is recorded and the latest examination will be carried forward in the analysis. In case of
553 drop-out before the first follow-up visit the participant will be excluded from the analysis. Participants are
only removed from the study if they decline participation.

554 9 Bias

555

556 We strive to minimize bias in our study. Minimally displaced fractures of the elbow can go unnoticed and
557 be missed by our project. However, Danish parents are usually not withholding in taking an injured child
558 to the ED. A strict protocol for referrals for treatment are in place in Denmark. All eligible patients
559 referred to Herlev and Gentofte University Hospital will be asked to participate in the study. We
560 speculate that by enrolling 50 participants the cohort will be representative of the background
561 population. We speculate that these efforts will limit selection bias. Efforts described in the follow-up
562 section reduce the risk of loss to follow-up. Overall, we find a low risk of bias in our study for the chosen
study design and size.

563 10 Benefits

564 Classifying lateral condyle fractures and establishing whether they are stable or not is the key to
565 choosing the right treatment strategy. MRI is the only feasible image modality that can make that
566 distinction.

567
568 LHCF is currently a fracture that requires open surgery in most cases due to the radiographic inability to
569 distinguish stable injuries from unstable. This project seeks to use MRI without sedation or GA in order
570 to distinguish fracture patterns. MRI has been shown to be feasible in all age groups without the need
571 for sedation or GA [24].

572
573 Thévenin-Lemoine et.al. found that 25 of 27 children could successfully complete an MRI without

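### Sections 6.2.9 and 8.3.1 give conflicting rules for children who leave early; if carry-forward reaches yes/no outcomes, late-complication proportions may be biased low

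*Protocol*

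**What the plan says.** Section 6.2.9 (Premature study termination) lists four reasons for ending participation early: withdrawn consent, protocol violation, the investigator's decision ("Investigator's discretion (e.g. patient noncompliance with CIP"), and loss to follow-up. Of the data it then says: "If patients are withdrawn from the study, any collected data will be censored. Censoring allows this". The sentence ends by saying that the data are thereby accounted for.

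Section 8.3.1 (Patient discontinuation) covers a participant who stops attending for any reason. The date and reason "for drop-out is recorded and the latest examination will be carried forward in the analysis". Anyone who drops out before the first follow-up visit is left out of the analysis. The section closes by saying that participants are "only removed from the study if they decline participation".

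Section 8.3 describes the analysis: "Baseline characteristics and outcomes recorded at scheduled FU assessments will be presented using" simple summary statistics, with frequencies and percentages for categorical variables.

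The outcomes affected are in section 5.2: "Report the number and proportion of fractures that displace secondarily and their treatment", the final treatment, and any early or late complications.

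**The concern.** A child whose parents withdraw consent falls under both sections. Censoring ends the child's contribution at the last observation, while carry-forward extends it to 24 months. The sections also disagree on who can be withdrawn. A child taken out for non-compliance is terminated under 6.2.9, but is not removable under 8.3.1.

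Censoring has meaning in an analysis of time to an event, and the protocol describes none. The assurance in 6.2.9 therefore has nothing behind it in this document.

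Section 8.3.1 does not limit carry-forward to scores. Applied to a yes/no outcome, it turns event-free when last seen into event-free at 24 months. This matters most for late complications. Section 4.3 notes that some develop years after an untreated injury. Section 13 says adverse events in the ISO 14155 sense are not collected, so the complication and displacement outcomes carry the safety description. Section 8.2 justifies 50 children partly by the expectation that frequent and serious complications will be found.

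**Working it through.** **Nothing to reproduce.** The protocol gives no drop-out rate and no precision calculation. The planned 50 children rest on the size of earlier studies and on expected representativeness (section 8.2).

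**Inputs from the protocol.**
- 50 children (section 6.1.4).
- Secondary displacement in the literature from 4% to more than 40%, expected near 4% here (section 11.3.1).
- Splinting for usually four weeks (section 6.3.6), possibly two weeks longer (Table 1 footnote).
- Risk of a missed appointment described as low, with no figure (section 6.2).

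**Assumptions.** A 24-month late-complication risk of 10%; 10% to 20% of children leaving, with 30% as an extreme; leaving unrelated to outcome.

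**Formula.** Let p be the true 24-month risk, d the share who leave after the first follow-up visit, and f the share of the risk still ahead when they leave. Under carry-forward:

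expected proportion = p(1 − d) + d·p(1 − f) = p(1 − d·f), so bias = −d·p·f.

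Events recorded before leaving are kept. Only later events are lost.

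**Late complications, p = 10%, risk accruing evenly.** Leaving at month t gives f = 1 − t/24, which is 0.875 at 3 months, 0.75 at 6 and 0.5 at 12.

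| Share leaving | Month | Reported proportion | Bias (points) | Children of 50 |
|---|---|---|---|---|
| 10% | 3 | 9.1% | −0.9 | −0.4 |
| 10% | 12 | 9.5% | −0.5 | −0.25 |
| 20% | 3 | 8.25% | −1.75 | −0.9 |
| 20% | 6 | 8.5% | −1.5 | −0.75 |
| 20% | 12 | 9.0% | −1.0 | −0.5 |
| 30% | 3 | 7.4% | −2.6 | −1.3 |

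With 20% leaving and all the risk ahead (f = 1), the bias is −0.20 × 10% = −2.0 points, or one child.

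**Displacement at the expected 4%.**
- d = 10%, f = 0.5: −0.2 points.
- d = 20%, f = 1: −0.8 points, or 0.4 of a child.
- All displacement during casting and leaving after it (f = 0): zero.
- At a 40% risk, d = 10% with f = 0.5 gives −2.0 points, and d = 20% with f = 1 gives −8.0. Those figures need much of the risk to lie after the child has left.

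**The same in counts.** Suppose all leavers go before any event occurs. A cumulative-incidence estimate then equals events divided by those remaining.
- 2 events: carry-forward 2/50 = 4.0%; against 2/45 = 4.4% if 5 leave, or 2/40 = 5.0% if 10 leave.
- 5 events: carry-forward 5/50 = 10.0%; against 5/45 = 11.1%, or 5/40 = 12.5%.
- If every leaver had the event: 7/50 = 14% and 12/50 = 24% with 2 observed events; 10/50 = 20% and 15/50 = 30% with 5.

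The average bias is modest. What the raw percentage hides is how many children were no longer being observed.

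**The case against.** **The text can be read more gently.** Section 6.2.9 may use censoring loosely, to mean keeping data up to withdrawal, and that would be compatible with carry-forward. It speaks of children who are withdrawn, whereas 8.3.1 speaks of those who choose to stop. The groups overlap but are not stated to be identical. This softens the conflict without removing it: withdrawn consent falls under both, and the disagreement on who can be removed remains.

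**A reader might infer that all early leavers are counted as event-free for two years, so that displacement, surgery and complication proportions are all biased low.** The protocol does not support that. It sets no denominator for these outcomes and no explicit rule for carrying forward a yes/no event. The last examination fits scores and angles more naturally. Children who leave before the first follow-up visit are excluded, and a child with a recorded event keeps it. Section 11.3.1 places displacement risk during non-operative treatment, so exits at 3 to 12 months would hardly touch displacement or the surgery that follows. If censoring meant discarding data, the direction would depend on why children leave.

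**The effect is small beside sampling error.** The exact 95% interval for 5/50 runs from about 3% to 22%. This is correct and keeps the point modest.

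**The analysis plan may hold the method.** That is possible, as only the protocol is at hand. It cannot be said that no time-to-event analysis exists, only that the protocol describes none. Two stated rules that conflict still need reconciling in the protocol.

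**Later events may be visible.** Section 14 seeks access to the health record until the project ends. The protocol does not commit to using it to find events in children who have left.

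**Conclusion.** The conflict between 6.2.9 and 8.3.1 stands, both on what happens to the data and on who counts as withdrawn, and censoring has no analysis in the protocol to act on.

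The bias is conditional. It arises only if the 8.3.1 rule is applied to yes/no outcomes. When leaving is unrelated to outcome, it is then downward or nil. For late complications it is about 0.5 to 2 points at an assumed 10% risk with 10-20% leaving and at least half of the risk still ahead. That is at most one child in 50; 30% leaving at 3 months would raise it to 1.3 children. For displacement and resulting surgery it is small or nil if these arise during casting, a timing the protocol suggests but does not state. Risk, drop-out and timing of leaving are all assumptions. This should be corrected, but it does not undermine the study.

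**What to change.** 1. Merge 6.2.9 and 8.3.1 into one rule that says who counts as withdrawn and what happens to their data.
2. State in 8.3.1 that carry-forward is not applied to event outcomes (displacement, surgery, complications).
3. For these outcomes, report the raw count with the number of children under observation at each visit. Beside it, give a cumulative incidence at 24 months, with time from injury, children censored at their last visit, and a 95% interval. Note the assumption that leaving is unrelated to outcome: if well children are the ones who stop attending, this estimate will be too high, which is why the raw count stays next to it.
4. Delete the censoring sentence for scores such as MEPS.

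The cost is a wording change and one simple extra analysis on visit data already collected. Reported late-event rates may come out slightly higher.
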